The patient can be included irrespective of the type and timing of systemic therapy. This trial accepts that randomized patients participate in other trial protocols testing new systemic therapies, e.g. inhibitors of CDK4 and CDK6 kinase activity like abemaciclib in the Monarch E trial. It is also accepted that the patient is included in trials testing loco-regional therapies, e.g. the SENOMAC trial and the

Skagen Trial 1.

TREATMENT PROTOCOL

The first version of the trial was designed as a randomized trial. The inclusion started 1/1-2020. Due to slow accrual, the steering committee has decided to change the trial per 30/6-2023 to a prospective trial of arm A without randomization. It is expected that a prospective trial design will make it feasible for more departments to participate

Treatment arm A

Delayed-immediate reconstruction:

Primary Surgery: Skin sparing mastectomy (nipple sparing if appropriate) and axillary surgery according to guidelines or protocol. Reconstruction with silicone implant or expander covered by pectoral muscle and mesh or matrix.

Delayed reconstruction: Final reconstruction with any reconstructive procedure – being it autologous or implant-based (one- or two-stage, +/- acellular dermal matrix (ADM)) – is performed 6-12 months after completion of chemotherapy and RT. Any contralateral procedure is allowed when doing the delayed surgery, but not in relation to the initial cancer surgery.

Patients, who will not have the second delayed procedure performed will be included in the analysis of 'intention to treat' group and not excluded from the study.

Treatment arm B

Delayed reconstruction:

Primary surgery: Total mastectomy and axillary surgery according to guidelines or protocol.

Delayed reconstruction: 6-12 months after completion of PMRT: final reconstruction with any reconstructive procedure – being it autologous or implant-based (one-or two-stage, +/- ADM). Any contralateral procedure is allowed at any time point after PMRT has been delivered.

This arm recruited patients between 1/1-2020 and 30/6-2023

Concerning post mastectomy radiation therapy (PMRT)

This issue is described in the new ESTRO consensus guidelines for target volume delineation in implant based reconstruction ²⁶.

In general, the tissue beneath the skin surface of the mammarian region is the clinical target volume in all cases.

Implant-based reconstruction and PMRT

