At the first consultation and in the written information about the trial the patient is informed that we want information from her patient file passed on to the trial regarding tumour characteristics, and also about her recurrence and survival status for 15 years after randomization and on events related to the reconstruction. If she has a recurrence we need data passed on from her patient file regarding when and where the recurrence took place. The tumour characteristics are: tumour histological type, size, lymph node status (how many removed and how many with metastasis and what type of metastasis), malignancy grade/ER/PR/HER2/Ki67 status, Q score, resection margin, and surgical procedure, radiation therapy, and systemic treatment. Also information about serious events like a new cancer, heart disease, lung disease and stroke is passed on from her patient file, because these events may be related to the radiation therapy. If an increased risk of any of these events is associated with one of the radiation therapies on trial, it will influence the decision on what is to be future standard therapy.

The patient will be informed that the consent provides the investigators of the study direct access to obtain the necessary information from medical records to conduct the investigation and follow-up.

OUTCOME

Primary endpoint

Any complication deeming *surgical intervention* necessary (excluding percutaneous drainage and antibiotic treatment for inflammation in cases without need for open drainage) within a period up to 1 year after the final reconstruction:

- Infection
- Hematoma
- Loss of implant/expander
- Necrosis
- Seroma

Secondary endpoints

- Necrosis not requiring surgical intervention
- Infection not requiring surgical intervention but antibiotic treatment
- Herniation at donor-site
- Patient's satisfaction and QoL evaluated by BREAST-Q – appropriate modules.
- Psycho-oncological endpoints evaluated by validated questionnaires:
 - Depression (Becks Depression Inventory, BDI)
 - Fear of cancer recurrence (Concerns About Recurrence

Questionnaire-3, CARQ-3)

- Timely initiation of adjuvant therapy
- Morbidity including lymphedema, capsular contracture and range of motion (ROM) of the shoulder
- Breast photos
- Recurrence
 - Local recurrence
 - Regional recurrence
 - Distant metastasis
 - Disease-specific survival
 - Overall survival
- Death including cause of death

Concerning cancer related endpoints

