During the active RCT it was found that some of the included patients did not wish for the delayed (autologous) reconstruction, but rather kept their primary implant. It therefore seems that the rate of capsular contracture is lower than originally expected, perhaps due to a more gentle radiation therapy in the protocol.

For the prospective study, all participants will be included in the analyses, but stratification for type of final reconstruction will be performed.

ETHICAL CONSIDERATIONS

This trial is being conducted according to the 5th version of the Helsinki Declaration. The trial can only start after the approval of the regional ethical committee for Region Midt.

The risk of complications and failure is increased in breast reconstruction after mastectomy in patients who have RT. This is well known but still more and more patients request and receive such procedures.

Patients participating in the present study will be informed that reconstruction combined with RT doubles the risk of complications no matter which treatment arm they belong to. Presumably, delayed-immediate reconstruction will lead to better results and a higher satisfaction to the patients than will delayed, secondary reconstruction if patients have a uncomplicated trajectory. Therefore, if delayed-immediate reconstruction can be performed without increasing other risks, it could turn out to be preferable, and that is what the present study aims to prove.

At present there is no firm evidence and no consensus on which procedure to preferre, but there is an international trend towards primary reconstruction also in this group of patients, and there is a risk that this approach will be routinely adopted before sufficient evidence is available, for which reason it is crucial to first explore this option through a study.

PUBLICATIONS

The results from this study will be published irrespective them being positive, negative, or inconclusive. After approval of the study from the local scientific committee, the study will be registered on www.clinicaltrials.gov according to current recommendations.

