APPENDIX

IIa	DBCG RT RECON Primary endpoints after first surgery
IIb	DBCG RT RECON Primary endpoints after second surgery
III	BDI Becks Depression Inventory
IV	CARQ-3 Concerns About Recurrence Questionnaire-3
V	Breast-Q Part I_A Questionnaire before mastectomy
VI	Breast-Q Part I_B Questionnaire before reconstruction
VII	Breast-Q Part II_A Questionnaire after mastectomy
VIII	Breast-Q Part II-B Questionnaire after reconstruction
IX	DBCG RT RECON Questionnaire (morbidity)
X	DBCG RT RECON Registration form (morbidity and cosmesis)
XI	DBCG RT RECON Manual for clinical photos

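### Stratifying the whole-window complication endpoint by type of final reconstruction would build in an artificial gap, because implant loss is both an endpoint event and a determinant of the stratum

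*Protocol*

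**What the plan says.** The sentence at issue closes Statistical Considerations: "all participants will be included in the analyses, but stratification for type of final reconstruction will be performed". Just before it, the protocol reports that some women in the randomised phase "did not wish for the delayed (autologous) reconstruction, but rather kept their primary implant". Keeping the implant is therefore an expected final state, although the strata are not defined.

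The primary endpoint (Outcome, Primary endpoint) is any of five listed complications needing surgical intervention, "within a period up to 1 year after the final reconstruction". One of the five is "Loss of implant/expander". The Appendix lists form IIa, "DBCG RT RECON Primary endpoints after first surgery", and a matching form IIb for the second surgery, so events after the first operation count.

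Under Treatment arm A, the final reconstruction "is performed 6-12 months after completion of chemotherapy and RT", by any autologous or implant-based procedure. Women who never have it "will be included in the analysis of 'intention to treat' group and not excluded from the study".

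The planned test is a one-sided exact test of the overall success proportion: 0.74 expected, 0.64 as the non-inferiority limit, 2.5% level, 178 patients.

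**The concern.** Stratification is harmless when the stratum is fixed before the outcome can occur. Here the order is reversed. First surgery comes first, then a period in which primary-endpoint events can happen, and only then the type of final reconstruction. One of those events, loss of the implant, decides which strata a woman can still enter: she cannot be counted among those who kept the primary implant.

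If the stratified outcome is the endpoint as defined, covering first surgery to one year after final reconstruction, losses are removed from the kept-implant stratum and placed in the others. The stratum rates then differ even if the type of final reconstruction has no effect on risk. A table of such rates invites the reading that keeping the implant is safer than going on to a second operation. The protocol sets no landmark and does not limit the stratified events to those after the final reconstruction, so nothing in it prevents this.

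**Working it through.** **The plan's own figure.** Exact binomial, n = 178, limit 0.64, expected 0.74. Rejecting with at least 127 successes gives a one-sided type 1 error of 0.0233 and power of 0.815. The stated 178 for 80% power at 2.5% is reproduced. This test uses the overall rate only.

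**Inputs for the stratified rates**
- Overall complication rate T = 26% (Statistical Considerations).
- L, the share losing the implant before final reconstruction: 13%, expander removal in the delayed-immediate cohort cited in the background; 21.9%, implant loss with radiotherapy in the register study cited under Risk to the Patient; 5% as an assumed low value. The 21.9% comes from immediate reconstruction and not all of that loss need precede a final reconstruction, so I treat it as an upper value.
- k, the share of women without loss who keep the implant: not given. Assumed 25%, 50% and 75%.

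**Model with no true effect of type.** Every woman without loss has the same risk q of another qualifying complication, whatever her final type:
- q = 1 - (1 - T)/(1 - L)
- rate if kept = q
- rate if not kept = [L + (1 - L)(1 - k)q] / [1 - (1 - L)k]

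**Worked case, L = 13%, k = 50%**
- q = 1 - 0.74/0.87 = 0.149
- not kept = [0.13 + 0.87 × 0.5 × 0.149] / [1 - 0.435] = 0.195/0.565 = 0.345
- gap = 34.5% - 14.9% = 19.6 points, with the overall rate still 26%

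| Loss L | Kept | Not kept, k = 25% / 50% / 75% | Gap (points) |
|---|---|---|---|
| 5% (assumed) | 22.1% | 27.2% / 29.5% / 35.7% | 5 to 14 |
| 13% (cited) | 14.9% | 29.1% / 34.5% / 46.8% | 14 to 32 |
| 21.9% (cited) | 5.2% | 31.0% / 39.3% / 55.3% | 26 to 50 |

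**Chance of an apparent finding.** With 178 women, L = 13% and k = 50%, the strata hold about 77 and 101 women. By normal approximation a comparison of them would give nominal p < 0.05 about 85% of the time, although nothing differs. At L = 5% and k = 50% it is about 20%.

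**Sensitivity to how strata are defined.** Suppose the strata are implant-based versus other, half of the women without loss end implant-based, and a share g of those with loss are re-implanted.
- implant-based rate = [(1 - L)kq + Lg] / [(1 - L)k + Lg]
- L = 13%, g = 25%: 0.0975/0.4675 = 20.9%, against 0.1625/0.5325 = 30.5% in the other stratum. The gap is about 10 points.
- g = 50%: both strata 26%. The gap is gone, because loss no longer predicts the stratum.

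**Check of the remedy.** A simulation with L = 13%, k = 50% and the other risk split equally before and after the landmark gives 14.9% versus 34.5% over the whole window. Counting only events after the landmark gives 7.8% in both groups. That equality follows from the assumed equal risk. It shows that the built-in artefact is removed, not that the groups become comparable.

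**The case against.** The best defence is that the confirmatory result is safe. The exact test concerns the overall arm A rate, all participants stay in, and no between-stratum test is announced. This stands. A reader might infer that the primary analysis is biased; it is not.

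A second defence is that the protocol does not say outright that the whole-window endpoint is what will be stratified, and forms IIa and IIb would permit a stage-specific table. The strata and event window could be settled in an analysis plan that is not shown. This also stands, and the point is conditional for that reason. But the protocol commits to the stratification and defines only one endpoint window, so applying the one to the other is the natural reading and would mislead.

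Three stronger readings are tempting, and the documents do not support them.
- That women who keep the implant are event-free in the first stage. They are free of loss only. Infection, haematoma, necrosis and seroma needing surgery can all occur with the implant in place, and in the table they still have a rate of 5% to 22%.
- That the 17% under Risk to the Patient is an implant-loss rate. It is a surgical complication rate among 24 irradiated women.
- That the remark "It therefore seems that the rate of capsular contracture is lower than originally expected" is already an example of this error. It is an inference from women's choices about a secondary endpoint, not a stratified complication analysis.

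Nor can it be said that the guideline would be steered wrongly. The DBCG decision described in the protocol is about offering delayed-immediate reconstruction, not about choosing between types of final procedure.

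**Conclusion.** The point holds in conditional form. The stratifier is fixed after first surgery and partly by a component of the primary endpoint, so stratum-specific or stratum-adjusted whole-window rates would differ without any true effect of type. At the two loss rates that the protocol cites, the artificial gap between kept and not kept is about 14 to 50 points, against a non-inferiority margin of 10 points; at an assumed 5% loss it is about 5 to 14 points.

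These sizes rest on the 26% overall rate, equal residual risk in all women without loss, a kept share of 25% to 75%, and kept-versus-not-kept strata. Under an implant-based-versus-other split with many re-implantations the gap shrinks or vanishes. The protocol also names patient wish as a reason for keeping the implant, so loss is not the only determinant. It should be corrected before analysis, but it does not threaten the main conclusion of the trial.

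**What to change.** Replace the stratification sentence with four statements:
1. The overall arm A complication rate is the only inferential result.
2. Complications from first surgery to final reconstruction (form IIa) are reported for all patients, not split by later type.
3. Complications after the final reconstruction (form IIb) are reported by defined type, counting only events after that operation. Women who keep the implant are counted from a pre-set landmark at a comparable time.
4. The by-type rates are descriptive, because patient choice and earlier complications still confound them.

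The cost is a few sentences and a little more analysis work. Fewer events will fall in each stratum, so the by-type rates will be less precise. Women who keep the implant have no second operation, so it should be checked that their later events are recorded: the contents of form IIb are not shown, and it may not be triggered for them.

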APPENDIX

IIa	DBCG RT RECON Primary endpoints after first surgery
IIb	DBCG RT RECON Primary endpoints after second surgery
III	BDI Becks Depression Inventory
IV	CARQ-3 Concerns About Recurrence Questionnaire-3
V	Breast-Q Part I_A Questionnaire before mastectomy
VI	Breast-Q Part I_B Questionnaire before reconstruction
VII	Breast-Q Part II_A Questionnaire after mastectomy
VIII	Breast-Q Part II-B Questionnaire after reconstruction
IX	DBCG RT RECON Questionnaire (morbidity)
X	DBCG RT RECON Registration form (morbidity and cosmesis)
XI	DBCG RT RECON Manual for clinical photos
